10.8.3.2. Duration of Response (iRECIST)

Duration of response (DoR) is defined as the time, in days, from the first of the 2 assessments required for confirmed iPR or iCR to the time of the iCPD or death due to underlying cancer.

The duration will be calculated (in days) as:

Date of first overall response of iCPD or date of death due to underlying cancer (whichever is first) – Date of first of the two assessments required for confirmed iCR or iPR.

The duration of response will be summarised by cohort using descriptive summaries, which will not account for censoring. Additionally, Kaplan-Meier curves will be produced for each cohort along with a table summarising the median and 25th and 75th percentiles of the duration of response, inclusive of censoring, for each cohort, including sub-cohort.

[Kaplan-Meier plot: y-axis = cumulative proportion of participants who still have response, x-axis = day, one line for each cohort, including sub-cohort, overlayed on the same plot].

Exclusion

If a subject does not achieve confirmed iCR or iPR they will be excluded from this analysis.

Censoring

If a subject does not experience iCPD or death due to underlying cancer their duration will be censored at the date of their last disease assessment.

If a subject dies due to a cause other than underlying cancer they will be censored at the date of death.

If a subject does not have a disease assessment after their assessment confirming their response as iCR or iPR they will be censored at the date of their last disease assessment.

If a subject initiates another cancer treatment prior to iCPD/death their duration of response will be censored at the last assessment prior to initiation of the alternative cancer treatment.

If a subject experiences iCPD or death immediately following 2 or more visits at which their response was missing or NE their duration of response will be censored at the time of their last assessment prior to missing/NE response.

10.8.3.3. *Progression Free Survival (RECIST)*

Progression-free survival (PFS) is defined as the time, in days, from the first date of treatment until the first date at which PD is experienced or the subject dies due to any cause. Only deaths that occur within 30 days of the last tumor assessment will be included.

The duration will be calculated (in days) as:

Date of first overall response of PD or date of death due to any cause (whichever is first) – Date of first treatment.

Progression-free survival will be summarised by cohort, and sub-cohort for cohort F, using descriptive summaries, which will not account for censoring. Additionally, Kaplan-Meier curves will be produced for each cohort, and sub-cohort for cohort F, along with a table summarising the median and 25th and 75th percentiles of the progression-free survival, inclusive of censoring, for each cohort, including sub-cohort.

[Kaplan-Meier plot: y-axis = cumulative proportion of participants who are progression free, x-axis = day, one line for each cohort, including sub-cohort, overlayed on the same plot].

Censoring

If a subject does not experience PD or death they will be censored at the date of their last disease assessment.

If a subject does not have a disease assessment after their first treatment they will be censored at the date of their first treatment.

If a subject initiates another cancer treatment prior to PD/death they will be censored at the last assessment prior to initiation of the alternative cancer treatment.

If a subject experiences PD or death immediately following 2 or more visits at which their response was missing or NE they will be censored at the time of their last assessment prior to missing/NE response.

10.8.3.4. *Progression Free Survival (iRECIST)*

Progression-free survival (iPFS) is defined as the time, in days, from the first date of treatment until the first date at which iCPD is experienced or the subject dies due to any cause. Only deaths that occur within 30 days of the last tumor assessment will be included.

The duration will be calculated (in days) as:

Date of first overall response of iCPD or date of death due to any cause (whichever is first) – Date of first treatment.

Progression-free survival will be summarised by cohort, and sub-cohort for cohort F, using descriptive summaries, which will not account for censoring. Additionally, Kaplan-Meier curves will be produced for each cohort, and sub-cohort for cohort F, along with a table summarising the median and 25th and 75th percentiles of the progression-free survival, inclusive of censoring, for each cohort, including sub-cohort.

[Kaplan-Meier plot: y-axis = cumulative proportion of participants who are progression free, x-axis = day, one line for each cohort, including sub-cohort, overlayed on the same plot].

Censoring

If a subject does not experience iCPD or death they will be censored at the date of their last disease assessment.

If a subject does not have a disease assessment after their first treatment they will be censored at the date of their first treatment.

If a subject initiates another cancer treatment prior to iCPD/death they will be censored at the last assessment prior to initiation of the alternative cancer treatment.

If a subject experiences iCPD or death immediately following 2 or more visits at which their response was missing or NE they will be censored at the time of their last assessment prior to missing/NE response.

10.8.3.5. *Overall Survival*

Overall survival (OS) is defined as the time from the first dose of study drug to death due to any cause.

For analysis of OS, all subjects will be followed for survival for up to 2 years, until withdrawal of consent, loss to follow up, or death, whichever occurs first. At the time of analysis of OS, any subjects who remain alive will be censored at the last date they were known to be alive.

The duration will be calculated (in days) as:

Date of death due to any cause – Date of first treatment.

Overall Survival will be summarised by cohort, and sub-cohort for cohort F, using descriptive summaries, which will not account for censoring. Additionally, Kaplan-Meier curves will be produced for each cohort, and sub-cohort for cohort F, along with a table summarising the median and 25th and 75th percentiles of the overall survival, inclusive of censoring, for each cohort, including sub-cohort.

[Kaplan-Meier plot: y-axis = cumulative proportion of participants who are alive, x-axis = day, one line for each cohort, including sub-cohort, overlayed on the same plot].

Censoring

If a subject is still alive at the end of follow-up they will be censored at the date they were last known to be alive.

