9. STUDY ANALYSIS SETS

The populations defined below will be reviewed against the study database at a DRM at the time of the Final Analysis. The database at this time will be nearly final (i.e., the meeting may result in further data queries/changes post meeting), so inclusion/exclusion of subjects from study populations defined at this meeting will be further checked (post meeting) against a final locked database and will then be finalised prior to reporting.

The following analysis sets are defined:

Population	Description
Safety Analysis Set	All subjects who received any amount of study drug. All safety analyses will be performed using the Safety analysis set.
Intention to Treat (ITT) Analysis Set	All subjects who signed an informed consent form and were enrolled into the study.
Response-Evaluable (RE) Analysis Set	The Response-Evaluable analysis set is a modified ITT analysis set defined as all subjects with measurable disease at baseline who received study drug and had at least one post-baseline response assessment or discontinued treatment due to disease progression (including death due to disease progression) within 16 weeks (+ a 2-week window) of the first dose of study drug. All efficacy analyses will be performed using the Response-Evaluable analysis set

10.PLANNED STATISTICAL METHODS

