10.8.2.3. Duration of Stable Disease

Duration of stable disease (DoSD) is defined as the time, in days, from the first date of treatment until the first date at which PD is experienced or the subject dies due to underlying cancer.

The duration will be calculated (in days) as:

Date of first overall response of PD or date of death from underlying cancer (whichever is first)
– Date of first treatment.

The duration of stable disease will be summarised by cohort using descriptive summaries, which will not account for censoring. Additionally, Kaplan-Meier curves will be produced for each cohort along with a table summarising the median and 25th and 75th percentiles of the duration of stable disease, inclusive of censoring, for each cohort, including sub-cohort.

[Kaplan-Meier plot: y-axis = cumulative proportion of participants who still have stable disease, x-axis = day, one line for each cohort, including sub-cohort, overlayed on the same plot].

Censoring

If a subject does not experience PD or death due to underlying cancer their duration will be censored at the date of their last disease assessment.

If a subject dies due to a cause other than underlying cancer they will be censored at the date of death.

If a subject does not have a disease assessment after their first treatment they will be censored at the date of their first treatment.

If a subject initiates another cancer treatment prior to PD/death their duration of stable disease will be censored at the last assessment prior to initiation of the alternative cancer treatment.

If a subject experiences PD or death immediately following 2 or more visits at which their response was missing or NE their duration of stable disease will be censored at the time of their last assessment prior to missing/NE response.

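### The SAP's PFS and iPFS drop any death more than 30 days after the last scan, although scans are 8 and later 12 weeks apart, so subjects with no missed scan can lose their event

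*SAP*

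**What the plan says.** SAP 10.8.3.3 (PFS) and 10.8.3.4 (iPFS) start time at first treatment and take as the event PD (iCPD for iPFS) or death from any cause. Both add: "Only deaths that occur within 30 days of the last tumor assessment will be included".

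The calculation lines that follow carry no such limit. For PFS the line reads "Date of first overall response of PD or date of death due to any cause (whichever is first", and for iPFS "Date of first overall response of iCPD or date of death due to any cause (whichever is first".

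Three censoring rules matter here:
- No post-treatment scan: "If a subject does not have a disease assessment after their first treatment they will be censored at the date of their first treatment".
- Assessment gap: "If a subject experiences PD or death immediately following 2 or more visits at which their response was missing or NE they will be censored". The censoring date is the last assessment before the gap.
- New anticancer therapy: "they will be censored at the last assessment prior to initiation of the alternative cancer treatment".

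Duration of stable disease (DoSD, SAP 10.8.2.3) has the same start date and counts "Date of first overall response of PD or date of death from underlying cancer (whichever is first", with no window.

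Protocol 6.1 and 8.2 schedule scans every 8 (±1) weeks through Week 48 and then at least every 12 (±1) weeks. Protocol 9.3.1 and the synopsis (Appendix 9) each define PFS twice. One definition is followed by an unfinished sentence about a 30-day limit on deaths, anchored to progression rather than to a tumor assessment. The other has no limit. SAP section 11 lists no change to PFS.

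**The concern.** The window is shorter than the planned gap between scans, so it removes deaths because of where they fall in a normal scan cycle and not because follow-up was poor. A subject censored because they died, in an endpoint that counts death, is informatively censored.

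The SAP also disagrees with itself:
- The calculation lines have no window, so two programmers could derive different event dates.
- The gap rule already deals with missed assessments. Two missed scans exceed 30 days, so under the window the death part of that rule has almost nothing left to act on.
- The Response-Evaluable set keeps subjects who "discontinued treatment due to disease progression (including death due to disease progression) within 16 weeks" of first dose. A subject in it who dies before any post-baseline scan can then be censored at first treatment and contribute nothing to the curve.
- No censoring date is given for an excluded death. The general rule covers subjects without PD or death, and these subjects died.

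At stake is the accuracy of the exploratory PFS and iPFS curves, medians and quartiles.

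**Working it through.** The plan states no PFS figure to reproduce. Its Simon figures (type I error 0.0468 and 0.0471, power 80.11% and 80.51%) recompute exactly, but they concern ORR and do not bear on this point.

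**Step 1. Share of a scan interval in which a death is not counted, (L − 30)/L.**
- 8 weeks: (56 − 30)/56 = 26/56 = 46% (39% at 7 weeks, 52% at 9).
- 12 weeks: (84 − 30)/84 = 54/84 = 64% (61% at 11 weeks, 67% at 13).

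**Step 2. One subject.** Scans on days 56 and 112, next due on day 168, cancer death on day 150. The gap is 150 − 112 = 38 days and no scan is missed. DoSD has an event at day 150. PFS has none.

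**Step 3. Direction.** Assume an excluded death is censored at the last assessment, or at first treatment if there is no post-baseline scan. Take ten subjects at risk after day 112. One dies on day 132 (20 days after the scan, counted) and one on day 150 (38 days, dropped).
- All deaths counted: 9/10 = 90.0% from day 132, then 8/10 = 80.0% from day 150.
- SAP rule: the second subject leaves at day 112, so the estimate is 8/9 = 88.9% from day 132 and stays there.

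From the dropped death onward the curve is higher, here by 8.9 points. Between the last scan and that death it can be slightly lower, here by 1.1 points, because the subject has already left the risk set.

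**Step 4. Size.** Simulation of 600,000 subjects per scenario:
- Latent progression is exponential and is detected at the next scan (every 56 days to day 336, then every 84).
- Death is independent and exponential, with its rate set so that deaths before detected PD are 10%, 20% or 35% of first events. The documents do not give this share, so it is assumed.
- The baseline scan is uniform over days −28 to −1.
- Kaplan-Meier PFS is read at day 183, all deaths counted against the SAP rule.

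| Latent median | Deaths 10% | Deaths 20% | Deaths 35% |
|---|---|---|---|
| 40 days (observed median 56) | +0.5 | +0.8 | +1.1 |
| 80 days | 20.3→21.8% (+1.4) | 17.3→20.0% (+2.7) | 12.6→16.8% (+4.1) |
| 180 days | 48.9→50.6% (+1.7) | 44.9→48.5% (+3.5) | 38.0→44.3% (+6.3) |

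Differences were taken before rounding. The 40-day row matches the only PFS data in the documents, medians of 56.0 and 57.5 days in the earlier study (protocol 1.2), which had a different population. At 80 days about 57% of deaths without PD are dropped, and at 180 days 55–56%. This exceeds 46% because before the first on-study scan the last assessment is the baseline scan.

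**Step 5. Variants that reduce the rise.**
- PFS uses the Response-Evaluable set. Of the dropped deaths, 51–60% (80-day) or 27–35% (180-day) precede the first post-baseline scan, and under SAP section 9 those subjects enter only if progression was the reason. If none enter, the rises are 0.8, 1.5 and 2.4 points (80-day) or 1.0, 2.0 and 3.6 (180-day). This is a lower bound, because progression deaths do qualify.
- Scans spread over ±1 week: 1.1, 2.1 and 3.2 points (80-day); 1.5, 3.2 and 5.7 (180-day).
- Half of the dropped deaths rescued by a termination or suspected-progression scan (an arbitrary fraction): 0.7 to 3.0 points over the 80- and 180-day scenarios.

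**Step 6. Planned medians (±1-week scans, all subjects).** At 80 days: 110→111, 106→109 and 63→106 days. At 180 days: 174→217, 170→173 and 150→169 days. Without the early dropped deaths: 111→111, 109→109 and 101→106; then 175→217, 172→173 and 164→169. Eight of these twelve move by 0 to 5 days. The large jumps occur where the curve crosses 50% on a plateau between scans. In the 40-day scenario the median moves by 0 to 2 days.

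**Step 7. One cohort of 15 (80-day).** Events lost: 15 × 5.7%, 11.4% and 20.1% = 0.9, 1.7 and 3.0 subjects. For scale, 3/15 event-free has an exact 95% CI of 4.3–48.1%.

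No separate iPFS size is claimed.

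**The case against.** The best defence is that little depends on this. The endpoints are exploratory, there is no formal testing, and the study ended early. The SAP plans curves, medians and quartiles rather than a 6-month landmark. In the scenario closest to the only PFS data in the documents the shift is about a point or less. DoSD and OS are reported on the same set without the window, so a reader can see the contrast. The limit also has a source in the protocol. And the calculation line can be read together with the sentence before it, with the last assessment as the natural censoring date.

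Most of this stands and sets the severity. It does not save the rule. The protocol's version is unfinished and sits beside a definition without a limit, and the SAP chose between them without recording it. DoSD omits deaths from other causes, so it does not replace PFS.

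Four stronger readings are tempting, and the documents do not support them:
- That every on-schedule subject who dies loses the event. Deaths within 30 days of a scan count.
- That every cohort is biased. Cohort D recruited nobody and Cohort B has no Response-Evaluable subjects (SAP Table 14.2.1 shell), so neither has a curve. A cohort without such a death is unchanged.
- That the curve is higher at every time point. Step 3 shows a small dip before the dropped death.
- That efficacy conclusions are undermined. ORR, the Simon decisions and OS do not use the rule.

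**Conclusion.** The concern holds, at low severity. The 30-day sentence removes any-cause deaths from PFS and iPFS in subjects with perfect scan adherence, and it conflicts with the SAP's own calculation lines, with DoSD and with one of the protocol's two definitions. Wherever such a death occurs, the curve from that date onward is raised.

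The rise in 6-month PFS is about 0.5–1.1 points if observed median PFS is near 56 days, 1.4–4.1 points at an 80-day latent median and 1.7–6.3 points at 180 days. It is smaller if early deaths fall outside the Response-Evaluable set or if off-schedule scans are common. These figures rest on the assumed 10–35% share of deaths without progression, on independent exponential times, and on censoring at the last assessment. In a single cohort the shift is below sampling error.

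**What to change.** Delete the 30-day sentence from SAP 10.8.3.3 and 10.8.3.4 and state instead:

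> A death without prior PD (iCPD for iPFS) is an event at the date of death, including a death before the first post-baseline assessment, unless the new-anticancer-therapy rule or the rule for 2 or more consecutive missing/NE visits applies; those rules take precedence.

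Reword the first-treatment rule in both sections:

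> A subject with no post-baseline assessment is censored at first treatment unless the subject has a death that counts as an event under the rule above.

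A death after two or more missed visits with no post-baseline scan is then still censored at first treatment. Make the same change to the first-treatment rule in DoSD (SAP 10.8.2.3) for deaths due to underlying cancer. Otherwise a cancer death before any scan would be a PFS event but could be censored at day 0 for DoSD.

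Record in SAP section 11 which of the protocol's two PFS definitions is followed. The 30-day version may be kept as a sensitivity analysis. The cost is a few sentences and a small amount of reprogramming, using death and scan dates already collected.

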If repeat imaging shows iRECIST confirmed disease progression (iCPD), subjects will discontinue treatment. However, if the subject is deriving benefit after iCPD is observed, an exception to continue study treatment must be approved by the sponsor's Medical Monitor. Subjects who have repeat imaging to confirm progression are not required to undergo the next scheduled tumor imaging if it is less than 4 weeks later.

If repeat imaging shows iRECIST stable disease (iSD), iRECIST partial response (iPR), or iRECIST complete response (iCR), imaging should be continued every 8 (± 1) weeks and the subject should continue on trial treatment.

Note that the date of progression to be used for all relevant efficacy endpoints will be based on first documentation of PD (ie, RECIST v1.1 date of PD), regardless of date of confirmation of PD for subjects who continue on treatment.

All radiographic evaluations performed on the study will be collected and held for a potential independent review. Details regarding initiating an independent review will be outlined in the statistical analysis plan (SAP).

Confirmed progression of disease is defined as one of the following:

Clinical deterioration with or without radiographic PD per RECIST v1.1 (See [Appendix 7](#)) will confirm progression of disease. Note, however, that radiographic evaluation should be conducted at the time of clinical signs and/or symptoms of PD whenever possible.

- In subjects without clinical deterioration at the time of a radiographic scan showing PD per RECIST v1.1, a second scan conducted at least 4 weeks later showing progression of disease as outlined below will confirm progression:
- An additional 10% increase in tumor burden with a minimum 5 mm absolute increase from time of initial PD. This includes an increase in the sum of diameters of all target lesions and/ or the diameters of new measurable lesions compared to the time of initial PD.

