9.3.1. Efficacy Analyses

Efficacy analyses will be performed separately for each cohort. RECIST 1.1 criteria will be used for the primary endpoint evaluation ([Eisenhauer et al., 2009](#)), and iRECIST will be used for the exploratory endpoint response evaluation ([Seymour et al., 2017](#)). The iRECIST endpoints are analyzed using the same statistical methodology and the results will be presented in the same ways for the corresponding RECIST 1.1 endpoints.

The primary efficacy endpoint is the ORR defined as the proportion of subjects who achieve confirmed CR or PR per RECIST v1.1. The best overall response is the best response recorded from the start of the treatment until PD. The smallest measurements recorded since the treatment started will be used as the reference for PD. Subjects with CR or PR are considered to have obtained objective response. Subjects with not-evaluable response (NE) are counted as non-responders. Exact 95% CI will be constructed for the ORR for each cohort.

Subjects with CR, PR or SD are considered to have achieved disease control. Disease control rate is defined as the proportion of subjects who have achieved CR, PR, and SD. Duration of response only applies to subjects whose best overall response is CR or PR and is defined as the number of days from the first documentation of objective tumor response to the date of first PD or death due to underlying cancer.

Duration of stable disease is measured from the start of the treatment (the first treatment date for non-randomized studies, the randomization date for randomized studies) until the date when the criteria for overall disease progression are first met.

Duration of response is the time from first evaluation showing CR or PR (response confirmation required at subsequent tumor assessment no earlier than 4 weeks after first evaluation showing CR or PR) to the time of the first subsequent evaluation showing PD or death. Only subjects who experience a confirmed CR or PR will be analyzed for DoR. Subjects who do not experience PD or death will be censored per the censoring rules in the statistical analysis plan.

Progression-free survival is defined as the number of days from Day 1 in Cycle 1 to the first documented progression or death due to any cause. Only deaths that occurred within 30 days of the last progression assessed.

Overall survival is defined as the time from the first dose of study drug to death due to any cause.

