13.2. List of Tables

Table Number	Table Title
14.1.1	Participant Disposition – All Subjects
14.1.2.1	Demography – Safety Analysis Set
14.1.2.2	Demography of Cohort F – Safety Analysis Set
14.1.3.1	Baseline Disease Characteristics – Safety Analysis Set
14.1.3.2	Baseline Disease Characteristics of Cohort F – Safety Analysis Set
14.1.4.1	Prior Cancer Treatments – Safety Analysis Set
14.1.4.2	Other Prior Medications – Safety Analysis Set
14.1.4.3	Concomitant Medications – Safety Analysis Set
14.1.5	Investigational Product Exposure – Safety Analysis Set
14.2.1	Response – (RECIST v1.1) – Response Evaluable Analysis Set
14.2.2.1	Duration of Response (RECIST v1.1) – Response Evaluable Analysis Set
14.2.2.2	Duration of Response (RECIST v1.1) – KM – Response Evaluable Analysis Set
14.2.3.1	Duration of Stable Disease (RECIST v1.1) – Response Evaluable Analysis Set
14.2.3.2	Duration of Stable Disease (RECIST v1.1) – KM – Response Evaluable Analysis Set
14.2.4	Response – (iRECIST) – Response Evaluable Analysis Set
14.2.5.1	Duration of Response (iRECIST) – Response Evaluable Analysis Set
14.2.5.2	Duration of Response (iRECIST) – KM – Response Evaluable Analysis Set
14.2.6.1	Duration of Stable Disease (iRECIST) – Response Evaluable Analysis Set
14.2.6.2	Duration of Stable Disease (iRECIST) – KM – Response Evaluable Analysis Set
14.2.7	Progression Free Survival (RECIST) – KM – Response Evaluable Analysis Set
14.2.8	Progression Free Survival (iRECIST) – KM – Response Evaluable Analysis Set
14.2.9	Overall Survival – KM – Response Evaluable Analysis Set
14.3.1.1	Overall Summary of Treatment Emergent Adverse Events – Safety Analysis Set

Table Number	Table Title
14.3.1.2	Treatment Emergent Adverse Events by System Organ Class and Preferred Term – Safety Analysis Set
14.3.1.3	Treatment Emergent Adverse Events by System Organ Class, Preferred Term and Severity – Safety Analysis Set
14.3.1.4.1	Treatment Emergent Adverse Events Related to Etigilimab by System Organ Class and Preferred Term – Safety Analysis Set
14.3.1.4.2	Treatment Emergent Adverse Events Related to Nivolumab by System Organ Class and Preferred Term – Safety Analysis Set
14.3.1.4.3	Treatment Emergent Adverse Events Related to Etigilimab and Nivolumab by System Organ Class and Preferred Term – Safety Analysis Set
14.3.1.4.4	Treatment Emergent Adverse Events Related to Etigilimab or Nivolumab by System Organ Class and Preferred Term – Safety Analysis Set

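### Progression-free survival censors unscanned early deaths at first treatment, so known early failures drop out of the Kaplan-Meier curves

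*SAP*

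**What the plan says.** - **Who is analysed.** SAP 9 (and Protocol 9.2) puts a treated subject with measurable disease in the Response-Evaluable set if the subject "had at least one post-baseline response assessment or discontinued treatment due to disease progression (including death due to disease progression) within 16 weeks", plus a 2-week window. It adds: "All efficacy analyses will be performed using the Response-Evaluable analysis set". The table list in SAP 13.2 confirms this for the endpoint at issue: "Progression Free Survival (RECIST) – KM – Response Evaluable Analysis Set".
- **What counts as an event.** Under SAP 10.8.3.3 the event is a recorded overall response of PD (confirmed immune PD in 10.8.3.4) or death from any cause. Both sections then count only deaths within 30 days of the last tumor assessment.
- **What is censored.** Both sections also say: "If a subject does not have a disease assessment after their first treatment they will be censored at the date of their first treatment". The same sentence is in SAP 10.8.2.3 for duration of stable disease, where the event is PD or death due to the underlying cancer and no 30-day limit applies.
- **The protocol.** Protocol 9.3.1 defines progression-free survival as "the number of days from Day 1 in Cycle 1 to the first documented progression or death due to any cause", followed by an incomplete sentence about deaths within 30 days. A second definition later in the same section has no such limit. SAP 11 lists no change on this point.

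**The concern.** The two rules work against each other. A subject with no post-baseline scan can be in the analysis set for one reason only: early failure. The censoring rule then removes that subject from every risk set, because someone censored at time zero is never at risk at a later event time. The subject is listed in the population but contributes nothing to the curve.

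The bias has one direction. Early failures leave, so the Kaplan-Meier curve, its quartiles and its median can only stay the same or look better. The cohorts are small, single-arm and without a comparator, so one or two such subjects can visibly move the curve. The same subjects still count as non-responders in ORR and, if they die, as events in overall survival. The progression-free curve would therefore rest on a more favourable subset than the results printed beside it.

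**Working it through.** **1. The plan's own figures.** No figure is stated for progression-free survival. The only design figures are those of the Simon designs (SAP 8). Summing P(X1 = x) × P(at least r − x responses in 19) over the stage-1 counts x that allow continuation gives 0.0468 and 80.11% for Type 1, and 0.0471 and 80.51% for Type 2, as stated. They concern ORR and do not change here.

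**2. Does the rule reach deaths?** The sentence before it in SAP 10.8.3.3 is limited to subjects with neither PD nor death; this one has no such condition. The two sentences after it (new cancer treatment; two or more missing or non-evaluable visits) both override a later PD or death. Read as written, an unscanned death is censored at day 0.

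**3. Does a narrow reading avoid this?** Suppose the rule covers only event-free subjects. The 30-day limit still applies, and the last tumor assessment of an unscanned subject is the baseline scan. Appendix 7 allows that scan up to 28 days before treatment.
- The window for a countable death closes between 30 − 28 = 2 and 30 − 0 = 30 days after first dose.
- The first scheduled scan is at week 8, day 56 after first dose. Of those 56 days, 56 − 30 = 26 to 56 − 2 = 54 fall outside the window.
- Up to the second scheduled scan (week 16, day 112), 82 to 110 of the 112 days fall outside.

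A death outside the window is not an event, so the subject returns to the no-assessment rule and to day 0. If baseline is not a qualifying assessment, no unscanned death can count at all.

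**4. Size.** Let k of N subjects be unscanned early deaths, all before time t, with no one else censored before the last of them.
- SAP rule: S(t) = S_scanned(t), with N − k at risk.
- Counted as events: S(t) = [(N − k)/N] × S_scanned(t).
- Ratio: N/(N − k). For 1 of 10, 10/9 = 1.11; for 4 of 20, 20/16 = 1.25; for 6 of 29, 29/23 = 1.26.

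If c other unscanned subjects stay censored at day 0, replace N by N − c.

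**5. Illustration.** Assumed: about 40% of scanned subjects have PD at Day 57, 25% at Day 113 and 15% at Day 169, in whole subjects; the k deaths are at Day 35.

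| N, k | Day 56: SAP / event | Day 57: SAP / event | Day 113: SAP / event |
|---|---|---|---|
| 10, 1 | 1.00 / 0.90 | 5/9 = 0.556 / 5/10 = 0.50 | 3/9 = 0.333 / 3/10 = 0.30 |
| 20, 2 | 1.00 / 0.90 | 11/18 = 0.611 / 11/20 = 0.55 | 7/18 = 0.389 / 7/20 = 0.35 |
| 20, 4 | 1.00 / 0.80 | 10/16 = 0.625 / 10/20 = 0.50 | 6/16 = 0.375 / 6/20 = 0.30 |
| 20, 5 | 1.00 / 0.75 | 9/15 = 0.60 / 9/20 = 0.45 | 5/15 = 0.333 / 5/20 = 0.25 |

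The median stays at Day 113 with k = 2 of 20. It moves from Day 113 to Day 57 with k = 5. With k = 4 the curve lands exactly on 0.50 at Day 57, so its median depends on the convention for ties.

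**The case against.** **The rule may be meant only for event-free subjects.** It can be read as a sub-case of the sentence before it, so precedence over death is arguably unstated and not wrong. That is fair as to intent, but step 3 shows the 30-day limit then removes most of the same deaths.

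**Few subjects should be affected.** Protocol 8.2 requires a response assessment at treatment termination unless one was done within 14 days or PD was already documented. It also allows scans whenever progression is suspected, and SAP 10.1.1 uses unscheduled data. This stands: those left are mainly early deaths and subjects too ill to scan. It does not make the number zero. In the earlier study's combination part, the lower 95% limits were 14 days for median progression-free survival and 19 days for median overall survival (Protocol 1.2).

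**The endpoints are exploratory and untested.** True for progression-free survival (SAP 7.3, 10.1.3). Duration of stable disease is secondary, also untested. The Kaplan-Meier shell shows numbers at risk, so a careful reader could notice the loss.

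**Stronger readings that the documents do not support.** A reader might infer from "Clinical deterioration with or without radiographic PD per RECIST v1.1" in Protocol 6.1 that every unscanned clinical progression is a missed event. But the same section dates progression for efficacy endpoints by first documented RECIST PD, and Appendix 7 classes deterioration without objective evidence as symptomatic deterioration. Leaving these subjects out of the main curve follows the protocol. Nor does Protocol 9.3.1 plainly count every death, because it carries its own incomplete 30-day sentence.

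**Conclusion.** The point holds for deaths, in progression-free survival by both criteria and in duration of stable disease. Subjects admitted to the set because they failed early are taken out of the curves at day 0, and the effect is always towards a more favourable curve. Its size is N/(N − k) where all k fail before the time in question; k is assumed throughout, and it should be small if termination-visit scans are done. In a cohort of 10, one such subject is worth a factor of 1.11.

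A reader might also infer that the trial's main result is biased. It is not. ORR and DCR keep these subjects in the denominator, overall survival counts their deaths, and the Simon rule uses response only. This is a correction that should be made to descriptive curves, not a threat to the primary analysis.

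**What to change.** In SAP 10.8.3.3 and 10.8.3.4:

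1. Apply day-0 censoring only to subjects with no post-baseline assessment who did not die before the second scheduled scan. Such a death follows at most one missed scan, so this agrees with the SAP's own rule on two or more missing visits.
2. Count a death before the second scheduled scan with no post-baseline assessment as an event on the death date, and exempt these deaths from the 30-day limit. Without the exemption, the first change has little effect.
3. Keep subjects who stopped for clinical progression, with no scan and no such death, censored at day 0 in the main curve. Count them as events on the discontinuation date in a sensitivity curve.
4. Make the matching change for deaths due to underlying cancer in SAP 10.8.2.3.
5. Report the number censored at day 0 by cohort.

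The cost is a few SAP sentences and one extra curve per progression-free survival endpoint. No new data are needed: withdrawal dates and reasons, death dates and causes of death are already in Listings 16.2.1.1 and 16.2.1.2. Reported progression-free survival becomes slightly less favourable.
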